2.3 Benefit/Risk Assessment

No significant medical risks to patients have been identified from studies conducted to date with ensifentrine administered in the nebulized, dry powder or metered dose inhalation formulations. With all formulations of inhaled ensifentrine studied to date (17 studies, n > 1300 patients), including nebulized suspension (15), DPI (1) and pMDI (1), including 2 x 4-week, 400-patient studies with nebulized ensifentrine in COPD patients up to twice daily doses of 6 mg, ensifentrine has been well tolerated to date, with adverse event (AE) incidence and severity generally similar to those in the placebo-treated group. In studies with COPD patients, this included patients with many underlying co-morbidities including cardiovascular disease, diabetes, hypertension and underlying renal dysfunction. Adverse events related to cardiovascular or gastrointestinal systems have not been associated with ensifentrine treatment. Serious adverse events (SAEs) have been uncommon and there is no apparent pattern in the SAEs reported to date. The risk of drug-drug interactions with ensifentrine is very low.

A small, transient increase in peak heart rate (HR) of 3 bpm was observed with the 6 mg nebulized dose after 4 weeks of twice daily treatment in patients with COPD, an increase in peak pulse rate (but not HR) of 6 bpm was observed with the 3 mg dose after 7 days of twice daily DPI treatment in patients with COPD, and an increase in peak heart rate was observed with the 3 mg and 6 mg single dose of pMDI of 7 beats per minute (bpm) and 11 bpm, respectively, in patients with COPD, but no corresponding increase in pulse rate was observed for the 3 mg dose. In healthy volunteers, a single dose of 6 mg nebulized ensifentrine showed an increase in peak HR of 12 bpm at supratherapeutic exposures. These small, transient increases in peak heart rate are not considered clinically meaningful and have not been associated with adverse clinical outcomes.

Ensisentrine has been demonstrated to have favorable non-clinical toxicology and PK profiles when delivered via the inhaled route as both a nebulized suspension and as a DPI. Following single dosing, the PK profiles from ensifentrine DPI and MDI are similar in patients with COPD.

Effects on reproductive performance in male rats given the highest dose of 15.5 mg/kg/day included lower number of pairings of dosed males resulting in pregnancy in undosed females, higher pre and post implantation loss resulting in lower mean litter size, and lower sperm motility and higher abnormal sperm. No ensifentrine-related adverse effects were observed at 5.75 mg/kg/day (20.5 times the maximum recommended human dose based on AUC). There were no effects on embryo-fetal survival and development in either rats or rabbits in the main embryo-fetal development studies. The effects of ensifentrine on fertility and reproductive performance in female rats have not yet been assessed.

Ensisentrine has statistically and clinically significant bronchodilator as well as anti-inflammatory effects. As such, the clinical development of ensifentrine is focused on the treatment of obstructive and inflammatory lung diseases, including COPD. Considering the consistent improvements in lung function, symptoms and health-related quality of life across multiple studies in patients with COPD and the overall favorable safety profile in studies to date, the benefit/risk profile of ensifentrine in patients with COVID-19 is considered positive.

More detailed information about the known and expected benefits and risks and reasonably expected AEs of ensifentrine can be found in the Verona Pharma plc. Ensifentrine Clinical Investigators Brochure v. 19, 20th May 2020.

3 OBJECTIVES AND ENDPOINTS

3.1 Objectives

3.1.1 Primary objective

The primary objective is to evaluate the effect of ensifentrine on the proportion of patients with recovery from COVID-19 over 29 days.

3.1.2 Secondary objectives

- To evaluate the effect of ensifentrine on COVID-19 related time to recovery, clinical status and risk of deterioration,
- To evaluate the effect of ensifentrine on hospitalization, non-invasive and invasive ventilation and oxygen use.

3.1.3 Safety objective

- To evaluate the safety and tolerability of ensifentrine in patients with COVID-19.

3.2 Endpoints

3.2.1 Primary endpoint

The primary endpoint is to evaluate the effect of ensifentrine on the proportion of patients with recovery (Day 29).

- Day of recovery is defined as the first day on which subjects satisfies one of the following two categories from the 7-point ordinal scale:
 - not hospitalized, no limitations of activities;
 - not hospitalized, limitation of activities, home oxygen requirement, or both.

3.2.2 Secondary endpoints

- Time to recovery defined as satisfying one of the following two categories from the 7-point ordinal scale (Day 1-Day 29):
 - not hospitalized, no limitations of activities;
 - not hospitalized, limitation of activities, home oxygen requirement, or both.
- Proportion of patients with recovery at Days 7, 14, 29 and 60.
- Proportion of patients with improvement (from Day 1) of one category using the 7-point ordinal scale at Days 7, 14 and 29.
- Proportion of patients with improvement (from Day 1) of two categories using the 7-point ordinal scale at Days 7, 14 and 29.
- All-cause mortality at Days 29 and 60.
- Proportion of patients alive and not in with respiratory failure (invasive mechanical ventilation or extracorporeal membrane oxygenation [ECMO]) at Day 29.
- Proportion of patients needing re-hospitalization over 60 days.
- Duration of hospitalization from Day 1 (Day 1 - Day 29; measured in days).

- Mean change from baseline in 7-point ordinal scale (Days 7, 14 and 29).
- Total time on supplemental oxygen (Day 1 - Day 29; measured in days).
- Incidence and duration of new non-invasive ventilation or high flow oxygen use (Day 1 - Day 29; measured in days).
- Incidence and duration of new oxygen use (Day 1 - Day 29; measured in days).
- Incidence and duration of new mechanical ventilator use (Day 1 - Day 29; measured in days).
- Proportion of patients receiving invasive mechanical ventilation or extracorporeal membrane oxygenation (ECMO) at Days 7, 14 and 29 (7-point ordinal scale criteria #6).

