10.4 Efficacy

The proportion of patients with recovery at Day 29 will be compared between treatment groups using a logistic regression model adjusting for treatment. The treatment difference will be expressed as an odds ratio with 95% confidence intervals and associated two-sided p-value. Potential stratification variables such as age group and/or gender may be considered depending on the randomization outcome, details will be given in the Statistical Analysis Plan.

The time to recovery from Day 1 to Day 29 will be compared between treatment groups using a log-rank test; patients not in recovery at end-of study/withdrawal will be censored at last observed time point in the treatment period or at last time status was assessed if collected post treatment-withdrawal. Patients with death as outcome will be censored at the scheduled end-of-study day 29. Data will be illustrated using Kaplan-Meier plots and

the median time to recovery estimated if appropriate. Stratification in the model with respect to age group and/or gender may be considered based on the randomization outcome.

Secondary endpoints of survival type will be compared between treatments using the log rank test similar to the time to recovery endpoint. Secondary endpoints assessing proportion of patients fulfilling an event will be compared between treatments using a logistic regression. Continuous outcomes will be compared between treatments using ANCOVA models with treatment and stratification groups as factors and baseline as a covariate. Estimated treatment difference with 95% confidence intervals and associated 2-sided p-value will be given. Endpoints assessing duration of (days with) additional oxygen use/ventilator need will be compared between treatments using Wilcoxon rank sum test.

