4 PREFACE

The SAP for "A SINGLE-CENTER, PILOT, RANDOMIZED, DOUBLE-BLIND, PLACEBO-CONTROLLED STUDY TO EVALUATE THE EFFICACY AND SAFETY OF ENSIFENTRINE IN THE RECOVERY OF HOSPITALIZED PATIENTS WITH COVID-19" describes and expands upon the statistical information presented in the protocol.

This document describes all planned analyses and provides reasons and justifications for these analyses. It also includes sample tables, listings, and figures planned for the final analyses.

Any deviation from this SAP will be described and justified in protocol amendments and/or in the clinical study report (CSR), as appropriate.

The reader of this SAP is encouraged to also review the study protocol for details on conduct of the study and the operational aspects of clinical assessments.

pg. 6 Confidential

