5.1 Purpose of the Analyses

This SAP encompasses the final analysis of primary and secondary outcome measures. These analyses will be included in the CSR.

This is a pilot study which will expand our knowledge and understanding about how ensifentrine can be used to facilitate recovery or prevent deterioration in hospitalized, COVID-19 patients.

pg. 7 Confidential

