	Total time of non-invasive ventilation or high flow oxygen use (post-dose Day 1	Clinical status assessed using the 7-point ordinal scale score.
	- Day 29; measured in days).	Non-invasive ventilation or high flow oxygen use = # days where the 7-point ordinal scale score
		is equal to 5 or 6. • Or 7-point ordinal scale score is equal to 7 if patient dies while hospitalized between Day 1-29.
	Proportion of patients alive and with oxygen use at Days 7, 14 and 29	Clinical status assessed using the 7-point ordinal scale score.
	,	The proportion of patients in each treatment arm that meet the definition of requiring oxygen use.
		Hospitalized patient supplemental oxygen = the 7-point ordinal scale score is equal to 4, 5, or 6. • Or 7-point ordinal scale score is equal
		to 7 if patient dies while hospitalized between Day 1-29.
		Not hospitalized patient supplemental oxygen = the 7-point ordinal scale score is equal to 2 (if required to have home oxygen).
	Proportion of patients alive at Days 7, 14 and 29 with non-	Clinical status assessed using the 7-point ordinal scale score.

pg. 16 Confidential

Endpoints		Definitions
	invasive ventilation or high flow oxygen use	The proportion of patients in each treatment arm that meet the definition of requiring non-invasive ventilation/high-flow oxygen use.
		Non-invasive ventilation or high flow oxygen use = the 7-point ordinal scale score is equal to 5 or 6. • Or 7-point ordinal scale score is equal to 7 if patient dies while hospitalized between Day 1-29.
	Proportion of patients alive and receiving invasive mechanical ventilation or extracorporeal membrane oxygenation (ECMO) at Days 7, 14 and 29).	Clinical status assessed using the 7-point ordinal scale score. The proportion of patients in each treatment arm that meet the definition of requiring invasive mechanical ventilation.
		The 7-point ordinal scale score is equal to 6. • Or 7-point ordinal scale score is equal to 7 if patient dies while hospitalized between Day 1-29.
Safety Refer to Section 9, Table 12	Incidence of Adverse Events (AEs).	Number of AEs and number of patients with AEs for all TEAEs and for subcategories of AEs (SAEs, severe AEs, fatal AEs etc). Incidence = proportion of patients in each treatment arm that experience an adverse

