9.4.2.1 Sub-sets based on post-randomization outcome

Descriptive summaries of the proportion of patients as well as the duration of the worsening following initiation of study medication will be provided for these endpoints:

- Proportion of patients needing re-hospitalization (post-dose Day 1 Day 60).
 - Applies to the sub-set of patients that were randomized, treated with study medication and discharged from the hospital alive then re-admitted to the hospital for COVID-19 related treatment.
- Proportion of patients and duration of new oxygen use (post-dose Day 1 Day 29; measured in days).
 - Applies to the sub-set of patients that were randomized and treated with study medication but then had a new need for supplemental oxygen (score worsened to 4, 5 or 6).
 - Or those which improved during hospitalization (to 3) and then their clinical status worsened again (to 4, 5 or 6).
- Proportion of patients and duration of new non-invasive ventilation or high flow oxygen use (post-dose Day 1 - Day 29; measured in days).
 - Applies to the sub-set of alive patients that were randomized and treated with study medication but then had a new need for non-invasive ventilation or highflow oxygen use (score worsened to 5 or 6).
 - Or those which improved during hospitalization (to 3 or 4) and then their clinical status worsened again (to 5 or 6)

The total number of days with recorded use will be the sum of all reported days, regardless of whether the days occur consecutively or in disjoint intervals.

9.4.3 Change from baseline in 7-point ordinal scale (Days 7, 14 and 29).

Change from baseline in 7-point ordinal scale will be compared between treatments using ANCOVA models with treatment and COVID disease severity state as factors and baseline as a covariate. Estimated treatment difference with 95% confidence intervals and associated 2-sided p-value will be given. Sub-group analysis will only be performed for sub-groups with a minimum size.

9.4.4 Total time on supplemental oxygen (Day 1 - Day 29; measured in days).

The total number of days with recorded use will be the sum of all reported days, regardless of whether the days occur consecutively or in disjoint intervals. Results will be summarized by descriptive statistics including medians and quartiles by treatment arm and compared between treatment groups using Wilcoxon rank sum test. Patients that do not reach the specified score on any day will be counted as 0 days.

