14.2.18	Proportion of patients receiving invasive mechanical ventilation or extracorporeal membrane oxygenation (ECMO, 7-point ordinal scale criteria #6) at Days 7, 14 and 29, ITT	Overall and by Treatment group Day 1 – Day 7 Day 1 – Day 14 Day 1 – Day 29

pg. 25 Confidential

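### The SAP has no analysis of the protocol's secondary endpoint on incidence and duration of new mechanical ventilation; episodes between Days 7, 14 and 29 are not tabulated as ventilation

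*Protocol*

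**What the plan says.** Protocol 3.2.2 (and the synopsis) lists three endpoints on the incidence and duration of new support over Days 1-29: oxygen, non-invasive ventilation or high flow oxygen, and mechanical ventilation. The third reads "Incidence and duration of new mechanical ventilator use (Day 1 - Day 29; measured in days"). The next bullet is a different endpoint, the proportion on invasive ventilation or "extracorporeal membrane oxygenation (ECMO) at Days 7, 14 and 29 (7-point ordinal scale criteria #6"). Protocol 10.4 gives the method for durations: "Endpoints assessing duration of (days with) additional oxygen use/ventilator need will be compared between treatments using Wilcoxon rank sum test".

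The SAP Preface states: "This document describes all planned analyses and provides reasons and justifications for these analyses". SAP 5.1 adds: "This SAP encompasses the final analysis of primary and secondary outcome measures".

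SAP 9.4.2.1 covers new oxygen use and "Proportion of patients and duration of new non-invasive ventilation or high flow oxygen use". It has no entry for new mechanical ventilation. SAP Table 5 defines the invasive ventilation endpoint at Days 7, 14 and 29 as "The 7-point ordinal scale score is equal to 6", with in-hospital death also counted. The matching output in SAP Table 11, 14.2.18, is "Proportion of patients receiving invasive mechanical ventilation or extracorporeal membrane oxygenation (ECMO, 7-point ordinal scale criteria #6") on the same three days.

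**The concern.** A listed secondary endpoint would go unanalysed by a team that followed the SAP exactly. It is not a peripheral one. Preventing progression to mechanical ventilation is a stated goal of treatment (Protocol synopsis and 4.2.1; SAP 5), and the effect on invasive ventilation is part of a secondary objective (Protocol 3.1.2; SAP 6.2).

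Status on three fixed days is not a substitute for incidence and duration over the whole window. The protocol lists the two as separate endpoints, and the daily scores needed for the second are already collected. Dropping an endpoint without a stated reason also leaves the final report open to a charge of selective reporting, whatever the power of the study.

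**Working it through.** There is no planned figure to reproduce: the study is unpowered (Protocol 10.3; SAP 8.1). The check is a trace of each endpoint, followed by an illustration.

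**Trace**

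| Protocol 3.2.2 endpoint | Definition or analysis in the SAP |
|---|---|
| New oxygen use, incidence and duration | 9.4.2.1, descriptive (worsened to 4, 5 or 6) |
| New non-invasive ventilation or high flow, incidence and duration | 9.4.2.1, descriptive (worsened to 5 or 6) |
| New mechanical ventilation, incidence and duration | None |
| Invasive ventilation or ECMO at Days 7, 14, 29 | Table 5; Table 14.2.18 |

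The total-time sections, SAP 9.4.4 to 9.4.6, cover oxygen, non-invasive ventilation and hospitalization only. SAP 8.5 nevertheless keeps a rule that counts a death as invasive ventilator need for the rest of the evaluation period. That wording suits a duration analysis, so the omission looks like an oversight.

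Two SAP outputs use interval wording. The contents column for Table 14.2.18 lists Day 1 to Day 7, 14 and 29, although Table 5, the table's own title and its shell all give status on a day. Table 14.2.10 (alive and not in respiratory failure) has similar interval rows, although Table 5 defines it at fixed days. Read cumulatively, the first could give an incidence and the second an incidence of ventilation or death combined. Neither gives a duration.

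**Where a score of 6 between the fixed days does appear**

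- New and total oxygen use, pooled as scores 4-6 (SAP Table 5, 9.4.2.1, 9.4.4).
- New and total non-invasive ventilation or high flow, pooled as scores 5-6 (SAP Table 5, 9.4.2.1, 9.4.5).
- Ordinal-scale plots over time (SAP 9.6) and by-patient daily listings (SAP 10).

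None of these summaries separates intubation from high flow oxygen. A patient who moves from 5 to 6 adds the same days to the 5-6 total as one who stays at 5.

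**Illustration: how often three fixed days miss an episode**

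Assumptions, none of them from the documents: one unbroken episode of L days in a surviving patient, with start day s uniform on Days 2-29 (28 start days). The episode is seen if Day 7, 14 or 29 lies in s to s+L-1.

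- L = 3: starts 5-7, 12-14 and 27-29 are seen, 3+3+3 = 9. Missed 19/28 = 68%.
- L = 5: starts 3-7, 10-14 and 25-29 are seen, 5+5+5 = 15. Missed 13/28 = 46%.
- L = 7: starts 2-7, 8-14 and 23-29 are seen, 6+7+7 = 20. Missed 8/28 = 29%.

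Protocol 10.1 gives windows for Days 7 and 14. On one reading, any of Days 6-8 or 13-15 counts, together with Day 29:

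- L = 3: 5+5+3 = 13 seen. Missed 15/28 = 54%.
- L = 5: 7+7+5 = 19 seen. Missed 9/28 = 32%.
- L = 7: 7+7+7 = 21 seen. Missed 7/28 = 25%.

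Onset matters. With start days uniform on Days 2-12 only (11 start days, fixed days without windows), 4/11, 8/11 and 11/11 episodes of 3, 5 and 7 days are seen. The missed shares are then 7/11 = 64%, 3/11 = 27% and 0%.

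**Scale.** One patient is 1/30 = 3.3 percentage points in the ensifentrine arm and 1/15 = 6.7 in the placebo arm. That is the weight of a single missed patient, not an estimate of bias.

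**The case against.** A reader might infer that ventilation between the three days is never counted at all. The documents do not support that. As traced above, such days enter the pooled 5-6 and 4-6 analyses, the plots and the listings. Protocol 7.1.1 also lists need for mechanical ventilation as a reason for withdrawal from study medication, so the event should surface in Table 14.2.2 (last day on study medication) and in the composite safety endpoint of SAP 9.5. There, however, it appears as a discontinuation and not as ventilation. The interval wording for Table 14.2.18 leaves a cumulative reading open.

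The missed shares rest on assumed onset and episode length. Under earlier onset the 7-day figure falls to zero. They illustrate the gap and do not estimate it.

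The contrast with the sibling endpoints is real but modest. They have text in SAP 9.4.2.1, yet neither has a row in Table 5 or a numbered output in Table 11, and 9.4.2.1 is descriptive only.

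Finally, this is one of many secondary endpoints in an exploratory pilot of about 45 patients. No primary result or error rate is affected.

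These points limit the claim. They do not supply the missing analysis: nothing in the SAP reports duration of invasive ventilation, and nothing clearly reports its incidence over Days 1-29.

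**Conclusion.** The point holds in a limited form. A protocol secondary endpoint tied to a stated treatment goal has no SAP definition, analysis or table, and the Wilcoxon comparison of ventilator days in Protocol 10.4 is dropped without explanation. This conclusion comes from the trace alone and needs no assumption.

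Its consequence is that an episode falling wholly between Days 7, 14 and 29 is not tabulated as mechanical ventilation. It would be wrong to say that it leaves no mark on the analysis. Under the assumptions shown, the missed share runs from 29% to 68% for episodes of 7 down to 3 days, from 25% to 54% with the visit windows, and from 0% to 64% with onset confined to Days 2-12. The SAP should be corrected, but the validity of the primary analysis is not in question.

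**What to change.** Add to the SAP text and to Table 11, derived from the daily scores:

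1. The number and proportion of ITT patients per arm with any score of 6 after first dose up to Day 29. Entry requires a score of 3, 4 or 5, so any later 6 is new.
2. Days at score 6 up to Day 29, compared by the Wilcoxon test of Protocol 10.4. Place this alongside SAP 9.4.4 to 9.4.6, because 9.4.2.1 is descriptive only.

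Show observed ventilation separately from the version that applies the SAP 8.5 death rule. Under that rule alone, a never-ventilated patient who dies on Day 5 would be credited with 29 - 5 = 24 ventilator days (Days 6-29), which is not new ventilator use. State the missing-data rule as well: the carry-forward for total time in SAP 8.5 names only oxygen and non-invasive ventilator care.

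State the limits of the source. Daily scores stop at discharge, and the follow-up contacts in Protocol 8.5 ask for the date and duration of a readmission, so ventilation during a readmission may not be captured.

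Reconcile the contents column of Table 14.2.18 with its title and shell. If the sponsor prefers not to analyse the endpoint, the SAP should say so and give the reason.

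The cost is one SAP paragraph and one table. The in-hospital daily data are already collected (Protocol 8.1 and 8.1.4). Few events are likely, so the result will be mainly descriptive.

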3.2.3 Safety Endpoints

- Incidence of Adverse Events (AEs)
- Vital Signs

4 STUDY DESIGN

4.1 Overall Design

The purpose of this study is to evaluate the effect of ensifentrine on the proportion of patients hospitalized with COVID-19 infection with recovery over 29 days.

This is a single center, randomized, double-blind, parallel group, placebo-controlled study to determine the efficacy and safety of ensifentrine 2 mg BID administered via pMDI added on to SoC treatment for COVID-19 infection compared to subjects receiving SoC plus placebo.

Patients 18 to 80 years of age must be hospitalized with a confirmed diagnosis of SARS-CoV-2 infection confirmed by PCR test and displays at least one of the following: Respiratory rate greater than 24, new cough, new atypical chest pain, new dyspnea, oxygen saturation <97% at rest, chest x-ray with new changes consistent with COVID-19 related airspace disease.

Patients meeting criteria for inclusion and none of the criteria for exclusion at randomization will be randomized to receive study medication until to hospital discharge or up to 29 days of treatment, whichever comes first. Patients will be randomized 2:1 to receive one of the following study treatments:

- Treatment Arm 1 (n=30): Blinded ensifentrine (2 mg) pMDI BID + Standard of Care treatment for COVID-19 infection
- Treatment Arm 2 (n=15): Blinded placebo pMDI BID + Standard of Care treatment for COVID-19 infection

Randomized patients will receive blinded ensifentrine or placebo twice daily, approximately 12 hours apart in the morning and evening, through 29 days or until discharge from hospital, whichever is first. Patients will self-administer 4 actuations (puffs) pMDI observed by study staff at each dosing event.

During the treatment period, patients will undergo all assessments and procedures as outlined in the SoA until hospital discharge. Patients completing treatment will complete a study contact (telephone or visit as required) within 4 to 10 days of discharge or early withdrawal. All enrolled patients will complete a telephone contact 26 to 32 days and 55-65 days following receipt of 1st dose of study medication for assessment of clinical status via the ordinal scale, need for re-hospitalization and vital status.

